6.1. Duration

At least 20 subjects per month are expected to be enrolled at each participating center. Each participating site may involve one or more wards, based on its distribution of subjects receiving opioid therapy.

The study is expected to last approximately 10-13 (10-12 months of enrollment plus 30 days from the last enrolled subject). Not all the participating centers will be active at the moment of enrollment start.

Each subject will be followed-up for a maximum period of 30 days.

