9.3. Subject Consent

The investigator or authorized designee must obtain written informed consent before any clinical study related activity takes place. Written informed consent must be obtained prior to administration of opioid medication. In addition, written informed consent must be obtained pre-operatively, if surgery is applicable.

Well in advance of the consent discussion, the subject should receive the EC/IRB approved Patient Information and Informed Consent Form. During the consent discussion, the investigator or his/her authorized designee must fully inform the patient of all aspects of the clinical study that are relevant to the patient's decision to participate in the clinical study. If a patient is illiterate, an impartial witness must be present during the entire informed consent discussion. All items addressed in the Patient Information and the Informed Consent Form must be explained. The language used shall be as non-technical as possible and must be understandable to the patient and the impartial witness, where applicable.

The patient must have ample time and opportunity to read and understand the Patient Information and the Informed Consent Form, to inquire about details of the clinical study, and to decide whether or not to participate in the clinical study. All questions about the clinical study should be answered to the satisfaction of the patient.

Neither the investigator, nor the investigation site staff shall coerce or unduly influence a patient to participate or to continue to participate in the clinical study. The informed consent process shall not waive or appear to waive the patient's rights.

When the patient decides to participate in the clinical study, the Informed Consent Form must be signed and personally dated by the patient and investigator or authorized designee. If applicable, the witness shall also sign and personally date the consent form to attest that the information in the Patient Information and Informed Consent Form was accurately explained and clearly understood by the subject, and that informed consent was freely given.

After all persons have signed and dated the Informed Consent Form, the investigator must provide the subject with a copy of the Patient Information and the Informed Consent Form.

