9.5. Enrollment

The point of enrollment is informed consent completed and inclusion/exclusion criteria are confirmed per the screening evaluation.

Data collected for enrolled subjects includes:

- Medical history (including surgical, apnea, substance use, and medical therapy such as oxygen use and opioid use)
- Demographic & Physical exam
- Vital signs
- Supplemental oxygen use
- Surgery information (post-surgical subjects only)

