9.6. Capnography Monitoring Period

Each subject will be clinically monitored through standard methods (as per clinical practice of the site). Additional continuous data from the Capnostream monitor will be collected for a maximum of 48 hours to identify potential indicators of respiratory depression.

Monitoring of capnography and pulse oximeter data with the Capnostream monitor will start after opioid therapy has been initiated for subjects that will receive their first opioid therapy dose while on the hospital ward. The monitoring period will start for subjects once they arrive on the ward, for those subjects where opioid therapy was initiated prior to arrival on the hospital ward.

Monitoring may be discontinued after a minimum of 4 hours from the last dose of opioid therapy received or if the subject is discharged from the hospital ward.

Monitoring duration may be determined in periods, as deemed clinically appropriate during opioid therapy. An example of monitoring split into three periods:

PRODIGY CIP

- Period 1: first 24 hours continuous monitoring after enrollment (mandatory).
- Period 2: 12 hours continuous monitoring (to be performed for guidance during the first night following Period 1, from 7pm to 7 am).
- Period 3: 12 hours continuous monitoring (to be performed for guidance during the second night following Period 1, from 7pm to 7 am).

The suggested monitoring setting for Periods 2 and 3 has been proposed to facilitate subject's motion during daytime, thus covering the nighttime period at higher risk of developing RD events⁶. The alarm feature of the monitoring device will be silenced and the screen information blinded. A periodic check during the monitoring period should be completed to ensure the etCO₂ filter line and SpO₂ sensor are appropriately fitted on the subject.

Apart from the capnographic monitoring, no other device or concomitant medications different from clinical practice may be used during PRODIGY Study.

The Monitoring eCRF will be completed to document:

- Care pathway (location/transfers within the hospital)
- Monitoring duration
- Vital signs
- Supplemental oxygen use
- Medications
- Product information

At the end of the monitoring period the subject will be treated according to the hospital clinical practice and remain in the study for a maximum period of 30 days from the start of opioid therapy.

9.7. 1-Month Follow Up

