A 1 Month Follow Up visit (performed by phone if subject has been discharged) will be performed at 30 days (± 10 days) from enrollment.

Complete the 1 Month Follow Up eCRF. In addition, complete the applicable eCRFs to collect information related to:

- Adverse Events, if applicable to understand if any occurrence such as ORADE occurrence or mortality.
- Healthcare resource utilization (including hospital length of stay, readmission rate and related primary diagnosis).

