13.4. Secondary Endpoints

Comparisons on all categorical variables will be done using the Chi-square test or the Fisher exact test or Cochran-Mantel-Haenszel test for trend for ordinal variables with 3 or more categories, as appropriate. Continuous variable parameter comparisons will be performed using t-test or Wilcoxon test according to the normal or non-normal distribution.

The rate of events will be computed and reported separately for each group, together with their 95% confidence intervals. Rates will be then compared by means of either a mixed Poisson model or a negative binomial regression model (if overdispersion is present).

The Sensitivity and Specificity, Positve predictive value (PPV) and negative predictive value (NPV), and the ROC curves will be used to visualize the accuracy of the IPI algorithms at different cutoffs in predicting episodes.

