7.10.2.1 Secondary endpoint#1

The secondary objective#1 will be evaluated comparing subjects that will develop RD versus patients that will not develop RD in terms of:

- Incidence of AE and actions taken.
- Healthcare resource utilization (including hospital length of stay, 30 days readmission rate and primary diagnosis upon readmission).
- Subject mortality at 30 days.

This secondary objective will be explained in the Health Economic Analysis Plan (HEAP).

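### Readmissions are collected to about day 30 from enrollment, with no clock started at discharge; if RD subjects stay longer, the readmission comparison is biased toward fewer readmissions after RD

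*SAP*

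**What the plan says.** SAP section 7.10.2.1 evaluates secondary endpoint 1 by "comparing subjects that will develop RD versus patients that will not develop RD in terms of" several outcomes. One of them is "Healthcare resource utilization (including hospital length of stay, 30 days readmission rate and primary diagnosis upon readmission"; 30-day mortality is another. The section defines neither day 0 nor the set at risk for readmission, and refers the objective to a HEAP that is not among the documents supplied.

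The timing comes from the protocol:

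- Section 9.5: "The point of enrollment is informed consent completed and inclusion/exclusion criteria are confirmed per the screening evaluation".
- Section 9.3: consent precedes opioid administration, and "written informed consent must be obtained pre-operatively, if surgery is applicable".
- Section 9.7: the contact that gathers readmissions "will be performed at 30 days (± 10 days) from enrollment". It is made by phone where the subject has already left hospital, so some subjects are expected still to be inpatients.
- Section 9.6: subjects "remain in the study for a maximum period of 30 days from the start of opioid therapy".
- Section 6.1: "Each subject will be followed-up for a maximum period of 30 days".

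On methods, Protocol section 13.4 gives chi-square, Fisher or Cochran-Mantel-Haenszel tests for categorical variables. For event rates it says: "Rates will be then compared by means of either a mixed Poisson model or a negative binomial regression model (if overdispersion is present". It states no exposure time and no offset. The only follow-up exposure in the SAP (section 7.8) is study exit minus enrollment, which includes inpatient days.

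**The concern.** A subject can be readmitted only after the index discharge. With a window that opens at consent and closes near day 30, each day of the index stay, pre-operative days included, removes one day at risk. A subject still in hospital at the contact, or who died there, has no time at risk, yet a crude proportion counts that subject as not readmitted.

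Length of stay and mortality are compared between the same two groups as readmission. The first shortens the readmission window and the second ends it. The protocol's background (section 4.1) says that opioid-related adverse events lengthen stay in post-surgical patients. If RD does the same, the RD group has less time at risk and will show fewer readmissions at an equal post-discharge hazard. A real excess could be masked, or an apparent benefit produced. This would remain if every contact fell exactly on day 30, so it is separate from the width of the visit window.

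**Working it through.** **Plan figures.** The documents give no readmission risk, length of stay, effect size or power for this comparison, so there is no plan figure for it to reproduce. The overall sample size does reproduce: 10 × 12 / 0.12 = 1000 for derivation; 1000 × 3/2 = 1500; 1500 × 1.10 = 1650. It serves here only to give group sizes: 0.12 × 1500 = 180 with RD and 1320 without.

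**Inputs.**
- W, day the window closes, counted from enrollment: 30, range 20 to 40 (Protocol 9.7).
- L, days from enrollment to index discharge: assumed 4 without RD, and 5, 7 or 10 with RD.
- p, true 30-day risk after discharge: assumed 10% in both groups, so no true difference.

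**Formula.** Days at risk = W − L. Cumulative hazard over 30 days H = −ln(1 − 0.10) = 0.1054. Observed proportion = 1 − exp(−H × ((W − L)/30)^k), with k = 1 for a constant hazard and k = 0.6 for a front-loaded (Weibull) hazard.

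**Results for W = 30.**

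| Stay (days) | Days at risk | Observed, k = 1 | Ratio to 4-day stay | Observed, k = 0.6 | Ratio to 4-day stay |
|---|---|---|---|---|---|
| 4 | 26 | 8.73% | 1.00 | 9.22% | 1.00 |
| 5 | 25 | 8.41% | 0.96 | 9.01% | 0.98 |
| 7 | 23 | 7.76% | 0.89 | 8.59% | 0.93 |
| 10 | 20 | 6.78% | 0.78 | 7.93% | 0.86 |

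The level is affected too: 8.73% against a true 10% is about 13% too low for a 4-day stay.

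**Sensitivity, 4 versus 7 days, constant hazard.** True risks of 5% to 15% leave the ratio at 0.89. Contact at day 20 gives 0.82 and at day 40 gives 0.92. Replacing fixed stays by lognormal ones with medians 4 and 7 (log-scale SD 0.7) gives 0.86.

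**Rate models.** With no offset, the rate ratio at equal hazard is 23/26 = 0.88. With enrollment-to-exit time as offset (30 days in each group) it is (23/30)/(26/30) = 0.88, so that offset corrects nothing. With log post-discharge days as offset and a front-loaded hazard (shape 0.7), the ratio becomes (23/26)^−0.3 = 1.04 for 4 versus 7 days and (20/26)^−0.3 = 1.08 for 4 versus 10. The bias is smaller but reversed.

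**Consequence with 180 versus 1320 subjects.** With no true difference, the chance of a significant finding of fewer readmissions after RD (two-sided 0.05 test, lower tail) is about 2% with equal stays. It is about 5% for an RD stay of 7 days and 12% for 10 days. A true 18% versus 10% (ratio 1.80) would be observed as 1.62 or 1.42 respectively.

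**The case against.** The strongest objection is that the definition may sit in the HEAP. Protocol section 13.4 is generic, never mentions readmission, and is silent on an offset rather than ruling one out. A reader might infer that the plan has chosen a crude comparison over exactly 30 days from enrollment and that its result is therefore biased. The documents do not support that. They leave the origin undefined, give windows that disagree, and defer detail to a plan we cannot see.

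The bias also needs a difference in stay that is nowhere quantified. The background statement concerns opioid-related adverse events in post-surgical patients. RD here is detected on a silenced, blinded monitor, and it includes asymptomatic episodes without action, which Protocol section 11 does not count as adverse events. It would go too far to say that RD subjects will necessarily show fewer readmissions.

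Precision limits the practical effect. About 14 to 16 RD readmissions are expected (180 × 0.0776 and 180 × 0.0873), so a 95% interval for the ratio runs very roughly from 0.6 to 1.7 times the estimate. A shift of 7% to 11% is small beside that.

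These points stand and make the concern conditional. They do not remove it. The HEAP can define person-time, but it cannot create a full 30 days after discharge when collection stops near day 30 from enrollment. The choice of analysis therefore matters, and the documents supplied do not make it.

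**Conclusion.** The concern holds in conditional form. Under the collection schedule as written, time at risk for readmission is shortened by the index stay, and nothing in the documents supplied corrects for this. If RD subjects stay longer, the comparison is biased toward fewer readmissions after RD. On the assumed figures the effect is slight for a 1-day gap (2% to 4% relative), worth correcting at 3 days (7% to 11%) and large at 6 days (14% to 22%). These sizes rest on an assumed 10% risk, an assumed 4-day stay without RD and a window closing on day 30; none of the gaps comes from the documents. The effect is confined to one component of a secondary endpoint. The derivation and validation of the risk score are untouched.

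**What to change.** In SAP section 7.10.2.1 and the HEAP:

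- Define the outcome as time from index discharge to first readmission, among subjects in the modified full analysis set who were discharged alive.
- Estimate cumulative incidence with death as a competing event and censoring at last contact. Compare the groups over the post-discharge period observed in both.
- Do not make a constant-rate offset the main method, since it over-corrects if readmissions cluster soon after discharge. Do not use enrollment-to-exit exposure as an offset.
- Report post-discharge days observed per group. Show subjects not discharged by last contact separately, not as free of readmission.
- Use all-cause readmission unless planned or unplanned status is recorded on the eCRF.
- Reconcile the windows in Protocol sections 9.6 and 9.7.

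Before adopting this, confirm that discharge and readmission dates are captured on the healthcare-utilization or serious adverse event forms. Protocol section 9.7 lists length of stay, readmission rate and diagnosis, but not dates. If the dates are there, the cost is wording and slightly more programming, and the result will be less directly comparable with a crude percentage. The change removes the unequal clock; it does not recover follow-up that was never collected.

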7.10.2.2 Secondary endpoint#2

The secondary objective#2 will characterize the predictive values of etCO₂, RR, SpO₂ and the IPI⁵ in predicting rORADE. To evaluate the predictive values of the Capnostream monitoring parameters for rORADE, the Sensitivity, Specificity, PPV and NPV will be calculated. rORADE events will be considered the Gold standard and the CS20p monitoring parameters as the measurement to be tested. The population used for this endpoint is PRDPS adjudicated as RD. All Clinical Events occurring during not monitored period will be reported but excluded from the table below. For each RD adjudicated by the CEC, the Capnostream monitoring will be checked if any of the parameter meets at least once the thresholds (RR \leq 6 breaths for \geq 3 minutes, SpO₂ \leq 85% for \geq 3 minutes, EtCO₂ \geq 60 mmHg for \geq 3 minutes or IPI < 3,4,5,6). The table below shows the distribution of the true and false positive and negative for each monitored parameter:

Test		Gold Standard		
Monitoring Parameter		ORADEs/RDs		
RR ≤ 5 breaths for ≥ 3 minutes		YES	NO	Tot
	YES	TP	FP	TP+FP
	NO	FN	TN	FN+TN
	Tot	TP+FN	FP+TN	N
Monitoring Parameter		ORADEs/RDs		
SpO2 ≤ 85% for ≥ 3 minutes		YES	NO	Tot
	YES	TP	FP	TP+FP
	NO	FN	TN	FN+TN
	Tot	TP+FN	FP+TN	N
Monitoring Parameter		ORADEs/RDs		
etCO2 ≤ 15 or ≥ 60 mmHg for ≥ 3 minutes		YES	NO	Tot
	YES	TP	FP	TP+FP
	NO	FN	TN	FN+TN
	Tot	TP+FN	FP+TN	N
Monitoring Parameter		ORADEs/RDs		
IPI <3		YES	NO	Tot
	YES	TP	FP	TP+FP
	NO	FN	TN	FN+TN
	Tot	TP+FN	FP+TN	N
IPI <4		YES	NO	Tot
	YES	TP	FP	TP+FP
	NO	FN	TN	FN+TN
	Tot	TP+FN	FP+TN	N
IPI <5		YES	NO	Tot
	YES	TP	FP	TP+FP
	NO	FN	TN	FN+TN
	Tot	TP+FN	FP+TN	N
IPI <6		YES	NO	Tot
	YES	TP	FP	TP+FP
	NO	FN	TN	FN+TN
	Tot	TP+FN	FP+TN	N
Monitoring Parameter		ORADEs/RDs		
Any Monitoring Parameter RR ≤ 6 breaths for ≥ 3 min or SpO2 ≤ 85% for ≥ 3 min or EtCO2 ≥ 60 mmHg for ≥ 3 min or IPI < 3,4,5,6		YES	NO	Tot
	YES	TP	FP	TP+FP
	NO	FN	TN	FN+TN
	Tot	TP+FN	FP+TN	N

Where:

- N will be all RDs adjudicated by the CEC.
- TP= true positive are all rORADEs and parameter over/below the threshold.
- FN= false negative are all rORADEs but no parameter over/below the threshold.
- FP= false positive are all no rORADE but parameter over/below the threshold.
- TN=true negative are all no ORADEs and no parameter over/below the threshold.

Measure of the accuracy will be:

- Sensitivity: $\{TP/(TP+FN)\}$,
- Specificity: $\{TN/(FP+TN)\}$,
- Positive predictive value: $\{TP/(TP+FP)\}$,
- Negative predictive value: $\{TN/(TN+FN)\}$

Table 27 – Sensitivity, specificity, PPV and NPV of RD and ORADE – PRDPS

Accuracy Measure	RR %(IC)	SpO2 %(IC)	etCO2 %(IC)	IPI(<3) %(IC)	IPI(<4) %(IC)	IPI(<5) %(IC)	IPI(<6) %(IC)
Sensitivity	X% (Y%-Y%)	X% (Y%-Y%)	X% (Y%-Y%)	X% (Y%-Y%)	X% (Y%-Y%)	X% (Y%-Y%)	X% (Y%-Y%)
Specificity	X% (Y%-Y%)	X% (Y%-Y%)	X% (Y%-Y%)	X% (Y%-Y%)	X% (Y%-Y%)	X% (Y%-Y%)	X% (Y%-Y%)
PPV	X% (Y%-Y%)	X% (Y%-Y%)	X% (Y%-Y%)	X% (Y%-Y%)	X% (Y%-Y%)	X% (Y%-Y%)	X% (Y%-Y%)
NPV	X% (Y%-Y%)	X% (Y%-Y%)	X% (Y%-Y%)	X% (Y%-Y%)	X% (Y%-Y%)	X% (Y%-Y%)	X% (Y%-Y%)
...

Figure 7 – Receiver Operating Characteristics curve for RR- PRDPS

Figure 8 – Receiver Operating Characteristics curve for SpO2- PRDPS

Figure 9 – Receiver Operating Characteristics curve for EtCO2- PRDPS

Figure 10 – Receiver Operating Characteristics curve for IPI<3- PRDPS

Figure 11 – Receiver Operating Characteristics curve for IPI<4- PRDPS

Figure 12 – Receiver Operating Characteristics curve for IPI<5- PRDPS

Figure 13 – Receiver Operating Characteristics curve for IPI<6- PRDPS

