7.1.3 Analysis Sets

The following subject sets will be used for the analysis:

- The Full Analysis Set (FAS) includes all patients enrolled in the study those sign Patient Informed Consent, fulfill the inclusion and exclusion criteria. The FAS will be used for safety evaluation.
- The Modified Full Analysis Set (MFAS) includes all patients enrolled in the study those sign Patient Informed Consent, fulfill the inclusion and exclusion criteria, start opioid therapy and monitored in the ward. Patients will not be excluded from the MFAS population even if prematurely stops, intermittent use or does not start the monitoring. Patients with major protocol deviations will be excluded from the MFAS. The MFAS will be used to evaluate the primary analysis.
- The Potential Respiratory Depression Population Set (PRDPS) includes all patients in the MFAS and have at least one Episode-File and/or Clinical Event to be adjudicated. The PRDPS will be used for secondary endpoint#2.

The following table shows how each population set will be used for analyses:

Population set	Baseline assessment	Primary and Secondary Endpoints (#1,#3)	Secondary Endpoint#2	Adverse Events
FAS	√			√
MFAS	√	√		√
PRDPS	√		√	

For those patients who have less than the minimum monitoring, or who drop out of the study, the analyses will include all data up to the point of their last data collection.

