7.10.2 Secondary endpoints

For secondary endpoints the MFAS population will be used for analysis.

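### SAP secondary endpoint #2 tabulates only RDs adjudicated by the CEC, so specificity, PPV and NPV for RD carry no information, those for rORADE hold only among RDs, and population, reference and thresholds conflict

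*SAP*

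**What the plan says.** Protocol 5.1.2 and 5.2.2 and SAP 4.2.2 set objective 2 as the predictive value of etCO2, RR, SpO2 and IPI for both RD and ORADE. The title of SAP Table 27 repeats both targets: "specificity, PPV and NPV of RD and ORADE".

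SAP 7.10.2.2 narrows this. It names rORADE as the gold standard and sets the population: "The population used for this endpoint is PRDPS adjudicated as RD". It then fixes the denominator: "N will be all RDs adjudicated by the CEC". TP, FP, FN and TN are all defined by rORADE status. The column headings of the 2x2 tables, however, read ORADEs/RDs. Events outside monitoring are handled by a clear rule: "All Clinical Events occurring during not monitored period will be reported but excluded from the table below".

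Other sections name other populations. SAP 7.1.3 says "The PRDPS will be used for secondary endpoint#2", and PRDPS patients are those in the MFAS who "have at least one Episode-File and/or Clinical Event to be adjudicated". SAP 7.10.2 says "For secondary endpoints the MFAS population will be used for analysis".

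Thresholds differ within 7.10.2.2. The lead-in text and the combined table use RR ≤ 6 ("Any Monitoring Parameter RR ≤ 6 breaths for ≥ 3 min") and etCO2 ≥ 60 only. The single-parameter tables use RR ≤ 5, and etCO2 ≤ 15 or ≥ 60.

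**The concern.** Specificity and NPV need people without the target condition. Admitting only RDs removes all of them when RD is the target. When rORADE is the target, it removes the large group of monitored patients who had no RD.

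The tables then answer a narrower question, namely which RDs are rORADEs, while the objective and the Table 27 label promise accuracy for RD and ORADE in the PRDPS. A reader of Table 27 could take a low specificity or NPV as a property of the monitor on the ward.

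The conflicts in population, reference standard and thresholds also mean that two programmers could produce different versions of Table 27 from the same data. Two further gaps add to this: a parameter counts if it crosses a single time, with no stated window, and the IPI cut-offs have no duration.

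**Working it through.** **1. RD as target, N = RDs only.** No patient is RD-negative, so FP = TN = 0.
- Specificity = TN/(FP+TN) = 0/0, undefined.
- PPV = TP/(TP+0) = 100%.
- NPV = 0/(0+FN) = 0% if any RD misses the threshold.
- Sensitivity = TP/(TP+FN) can be computed, but the SAP defines TP and FN by rORADE alone.

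This is algebra and needs no assumption.

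**2. The plan's own figures.** SAP section 6 gives minimum incidences of RR 1.4%, SpO2 10% and etCO2 1%; Protocol 13.1 calls the last arbitrary. Under independence the union is 1 − 0.986 × 0.90 × 0.99 = 0.1215, which reproduces the stated 12%. Then 120/0.12 = 1000, 1000/(2/3) = 1500, and 1500 × 1.10 = 1650.

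**3. Patients left out.** 1500 × 0.88 = 1320 evaluable patients have no RD and enter no table.

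**4. SpO2 specificity for rORADE.** Assume independence, few rORADEs, equal CEC confirmation across triggers and no other triggers.
- All monitored patients: 1 − 0.10 = 90%.
- RDs only: 1 − 0.10/0.1215 = 17.7%.

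Apnea and clinical events are also routes to RD. If a share s of RDs comes only from other routes, specificity among RDs is s + (1 − s) × 0.177, which is 38% at s = 0.25 and 59% at s = 0.50. The documents do not give s.

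**5. NPV for rORADE.** Same inputs, counted per patient with N = 1500: 0.1215 × 1500 ≈ 182.2 RDs, 150 SpO2 crossers, and so 32.2 RDs without an SpO2 crossing. Assume rORADE in 1% (15 patients) and SpO2 sensitivity of 80% or 50% (FN = 3 or 7.5).

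| | Sensitivity 80% | Sensitivity 50% |
|---|---|---|
| Among RDs, missed rORADEs cross another threshold | 1 − 3/32.2 = 90.7% | 1 − 7.5/32.2 = 76.7% |
| Among RDs, missed rORADEs cross none | 32.2/35.2 = 91.5% | 32.2/39.7 = 81.1% |
| All monitored | 1 − 3/1350 = 99.8% | 1 − 7.5/1350 = 99.4% |

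The rORADE rate is not given. Protocol 4.1 reports intervention rates of 0.3% to 3.4%. With these as proxies at 80% sensitivity (FN = 0.9 or 10.2), NPV among RDs is 97% at 0.3%, and 68% (another threshold crossed) or 76% (none crossed) at 3.4%. In all monitored patients it is 99.9% and 99.2%.

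**6. PPV.** If every SpO2 crossing is confirmed as RD, PPV is the same in both populations: 12/150 = 8% or 7.5/150 = 5%. If only half of the non-rORADE crossings are confirmed, PPV among RDs is 12/(12+69) = 14.8% or 7.5/(7.5+71.25) = 9.5%, against 8% or 5%. Crossings that trigger no episode (an IPI dip, or RR of 6) never reach the CEC as device episodes, so they can also separate the two.

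**7. Sensitivity for rORADE.** An rORADE is itself an RD criterion (SAP 7.10.1), so monitored rORADEs should nearly all be in the table. Sensitivity is largely unaffected.

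**8. Would the full PRDPS cure it?** No. It still leaves out patients with neither an Episode-File nor a clinical event, who are the main source of true negatives.

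**The case against.** Several points on the other side stand.

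- A reader might infer that no accuracy measure for RD can be obtained. That is too strong: sensitivity can be computed among RDs. It would be flattered, because the same thresholds guide the adjudication.
- A reader might treat confirmed-only as settled. The SAP uses RD and adjudication loosely: 7.4 speaks of the CEC adjudicating patients with at least one RD, and 7.10.1 of adjudicating potential RDs. Confirmed RDs is the most natural reading, and step 8 shows that the wider one does not repair the tables.
- The three populations are nested, the 7.10.2 sentence is a general lead-in, and the restriction is stated openly in 7.10.2.2. This is a matter of reconciling text, but the Table 27 label still omits the restriction.
- Narrowing to rORADE has a rationale. RR, SpO2 and etCO2 are RD criteria, so an RD table is partly circular for them. That calls for a stated caveat. It does not remove RD from the objective.
- A reader might put the 21% and 41% in Protocol 4.1 into step 4. Those are RD incidences under wider definitions, with thresholds not given there, and are not crossing rates for these parameters.
- A reader might infer a known bias in specificity. The trigger mix is not given, so the figures show direction and possible size only. They also count patients, whereas N in the SAP counts RDs.

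**Conclusion.** The concern holds. As written, endpoint #2 yields no informative specificity, PPV or NPV for RD, and this follows from the table definition alone. For rORADE, specificity and NPV are conditional on already having RD; PPV is too, if some crossings are not confirmed or trigger no episode.

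The numerical gap is illustrative: SpO2 specificity of about 18% (38% to 59% with other triggers) against 90%, and NPV of 77% to 91.5% against 99.4% to 99.8%. It rests on independence, equal CEC confirmation across triggers, a 1% rORADE rate and 50% to 80% sensitivity. Nothing can be derived for etCO2 ≤ 15 or for IPI.

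The conflicts in population, reference standard and thresholds are plain in the text. A reader might extend the problem to the risk score, but the primary analysis does not use these tables, and the documents set no precision target for this endpoint. The change should be made; the study's main result does not depend on it.

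**What to change.** For endpoint #2 only:

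- **Population.** In 7.1.3, 7.10.2.2 and Table 27, specify MFAS patients with monitoring data, one row per patient. Note the exception in 7.10.2, so that endpoints #1 and #3 stay on the MFAS, which keeps patients who never started monitoring.
- **Tables.** Report sensitivity, specificity, PPV and NPV separately for rORADE yes/no and for CEC-confirmed RD yes/no, and make the column headings match.
- **Caveats.** State incorporation bias in the RD table for RR, SpO2 and etCO2. Describe whole-period tables as association, because a crossing may follow the event.
- **Unmonitored events.** Keep them reported but excluded. List patients whose only event fell in unmonitored time and leave them out; do not count them as event-free.
- **Existing table.** The present rORADE table may stay if labelled as conditional on RD.
- **Definitions.** Reconcile the RR and etCO2 thresholds between text and tables (no view is taken here on which is right). State the window in which a crossing counts and the duration rule for IPI.

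The cost is a rewrite of one SAP section and its table shells, with matching edits in 7.1.3 and 7.10.2, and a re-run of the threshold and IPI checks on stored device data. No extra adjudication is needed: device data are kept for each subject (Protocol 15.2.2), and the CEC already adjudicates all clinical events and stops device review only once a first RD is found (SAP 9.4).
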